11.0 Management and Reporting of Complaints

A Complaint is any written, electronic, or oral communication that alleges deficiencies related to the physical characteristics, identity, quality, purity, potency, durability, reliability, safety, effectiveness, or performance of a product after it is released for distribution.

11.1 Medical Complaints

11.1.1. Adverse Event Definition and Serious Adverse Event Categories

An adverse event (AE) is defined as any untoward medical occurrence in a patient, which does not necessarily have a causal relationship with their treatment. An adverse event can therefore be any unfavorable and unintended sign (including an abnormal laboratory finding), symptom, or disease temporally associated with the use of a medicinal product, whether or not the event is considered causally related to the use of the product.

Such an event can result from use of the drug as stipulated in the labeling, as well as from accidental or intentional overdose, drug abuse, or drug withdrawal. Any worsening of a pre-existing condition or illness is considered an adverse event.

This protocol requires all SAEs as outlined in this section to be actively solicited. The safety profile of adalimumab which has over 3.5 million patient years of post-marketing exposure is stable and well established; non-serious events will not be actively solicited as these events are not likely to contribute to the further understanding of the safety profile of the product. Any non-serious AEs will be collected as spontaneous reports if AbbVie is notified.

If an adverse event meets any of the following criteria, it is considered a serious adverse event (SAE):

Death of Patient:	An event that results in the death of a patient.
Life-Threatening:	An event that, in the opinion of the investigator, would have resulted in immediate fatality if medical intervention had not been taken. This does not include an event that would have been fatal if it had occurred in a more severe form.

Hospitalization:	An event that results in an admission to the hospital for any length of time. This does not include an emergency room visit or admission to an outpatient facility.
Prolongation of Hospitalization:	An event that occurs while the study patient is hospitalized and prolongs the patient's hospital stay.
Congenital Anomaly:	An anomaly detected at or after birth, or any anomaly that results in fetal loss.
Persistent or Significant Disability/Incapacity:	An event that results in a condition that substantially interferes with the activities of daily living of a study patient. Disability is not intended to include experiences of relatively minor medical significance such as headache, nausea, vomiting, diarrhea, influenza, and accidental trauma (e.g., sprained ankle).
Important Medical Event Requiring Medical or Surgical Intervention to Prevent Serious Outcome:	An important medical event that may not be immediately life-threatening or result in death or hospitalization, but based on medical judgment may jeopardize the patient and may require medical or surgical intervention to prevent any of the outcomes listed above (i.e., death of patient, life threatening, hospitalization, prolongation of hospitalization, congenital anomaly, or persistent or significant disability/incapacity). Additionally, any elective or spontaneous abortion or stillbirth is considered an important medical event. Examples of such events include allergic bronchospasm requiring intensive treatment in an emergency room or at home, blood dyscrasias or convulsions that do not result in inpatient hospitalization, or the development of drug dependency or drug abuse.

11.1.2 Severity

The following definitions will be used to rate the severity for any adverse event being collected as an endpoint/data point in the study and for all serious adverse events.

Mild:	The adverse event is transient and easily tolerated by the patient.
Moderate:	The adverse event causes the patient discomfort and interrupts the patient's usual activities.

Severe: The adverse event causes considerable interference with the patient's usual activities and may be incapacitating or life threatening.

11.1.3 Relationship to Pharmaceutical Product

The following definitions will be used to assess the relationship of the adverse event to the use of product:

Reasonable Possibility An adverse event where there is evidence to suggest a causal relationship between the product and the adverse event.

No Reasonable Possibility An adverse event where there is no evidence to suggest a causal relationship between the product and the adverse event.

If no reasonable possibility of being related to product is given, an alternate etiology must be provided for the adverse event.

11.1.4 Adverse Event Collection Period

Adverse events will be reported to AbbVie from the time the physician obtains the patient's authorization to use and disclose information (or the patient's informed consent) until 70 days following the intake of the last dose of physician-prescribed treatment will be collected, whether solicited or spontaneously reported by the subject. In addition, serious adverse events will be collected from the time the subject signed the study-specific informed consent. Adverse event information will be collected and recorded on the appropriate eCRFs.

Subjects will be contacted approximately 70 days following the intake of the last dose of physician-prescribed treatment for an assessment of any new or ongoing AEs.

All SAEs, as defined by AbbVie, reported during the 70-day follow-up phone call must be captured in the clinical database.

11.1.5 Adverse Event Reporting

In the event of a serious adverse event, and additionally, any non-serious event of malignancy in subjects/patients 30 years of age and younger, whether related to AbbVie product or not, the Investigator will notify the AbbVie Emergency contact person

(Taiwan ASR) identified at the beginning of the protocol within 24 hours of the physician becoming aware of the event.

11.1.6 Pregnancy Reporting

Pregnancy in a study subject must be reported to AbbVie within 1 working day of the site becoming aware of the pregnancy. Subjects who become pregnant during the study must be discontinued (Section 9.2.6). Pregnancies will be collected from the date of the first dose through 150 days following the last dose of adalimumab.

Information regarding a pregnancy occurrence in a study subject and the outcome of the pregnancy will be collected.

Pregnancy in a study subject is not considered an AE. However the medical outcome of an elective or spontaneous abortion, stillbirth or congenital anomaly is considered a SAE and must be reported to AbbVie within 24 hours of the site becoming aware of the event.

12.0 Plans for Disseminating and Communicating Study Results

At the end of this observational study, a report will be written by AbbVie or a CRO working on behalf of AbbVie. The required standard study report template will be followed. This report will contain a description of the objectives of the study, the methodology and its results and conclusions. The completed eCRFs, [patient questionnaires, interim assessments], the final study output and study report are the confidential property of AbbVie and may not be released to unauthorized people in any form (publications or presentations) without express written approval from AbbVie. The study results will be submitted to local authorities per local laws and regulations.

The results of this PMOS may be published by AbbVie or by any one of the participating investigators after agreement with AbbVie.

12.1 Ethical and Legal Consideration

All participant data will be handled in a manner compliant with all local regulatory and privacy laws. All parties will ensure protection of subject personal data and will not include subject names on any sponsor forms, reports, publications, or in any other disclosures, except where required by law. Appropriate role-based access to minimum necessary information will be maintained so that only authorized individuals have access to protected health information (PHI).

AbbVie shall comply with all applicable laws regarding the reporting of spontaneous adverse events (AEs) to the relevant local authorities in Taiwan. AbbVie will follow the

International Conference on Harmonization of Good Clinical Practice (ICH-GCP) guidelines for AE reporting and report all spontaneously reported AEs within the required timeframe (usually within 24 hours of discovery).

All IMS staff working directly with patient data and/or having direct contact with healthcare practitioners will have received formal training to ensure they have a clear understanding of how to recognize an AE and inform Affiliate Safety Representative so that they are in full compliance with local laws regarding AE reporting.

The study will be reviewed and approved by the appropriate Ethics Committee(s) at each site prior to the start of patient recruitment, according to the specific legal requirements in Taiwan.

12.2 **Confidentiality**

12.2.1 **Patient confidentiality**

Information on patients' identity shall be considered as confidential for all effects and purposes. Each site and patient will have a code in the study. Sites will be automatically coded by IMS. Patients will be assigned a sequential number by the site coordinator upon meeting all inclusion and no exclusion criteria.

The patients' identity should not be revealed nor published under any circumstances. Patient data recorded in the CRF will be documented anonymously, coded with a patient number in such a way that only the investigator and site staff may associate particular data with an identified or identifiable individual or his/her medical record. All other parties involved in data management, analysis and storage will receive, and subsequently analyze, non-identifiable patient data.

12.2.2 **Data confidentiality**

By signing the investigator's confidentiality agreement, the investigator affirms to AbbVie/IMS that information furnished by AbbVie/IMS to the investigator will be kept in confidence and such information will be divulged to any expert committee, affiliated institution, and employees only under an appropriate understanding of confidentiality with such committee, affiliated institution and employees.

12.3 **Study administration**

The entire study will be managed by an international project coordinator at IMS Japan K.K. who will coordinate the project and maintain fluid communication with the study sponsor, the study team and the director at IMS Japan K.K.

As part of the monitoring plan, regular phone calls (at least every two weeks) will be made between IMS and local site coordinator in order to check inclusion status, resolve any issues, check data plausibility, etc.

12.4 **Investigators compliance**

By signing the investigator's agreement, the investigator agrees to conduct the study in an efficient and diligent manner and in conformance with this protocol, generally accepted standards of good clinical practice and all applicable laws, rules and regulations relating to the conduct of the study.

The investigator shall prepare and maintain complete and accurate study documentation in compliance with applicable national and local laws, rules and regulations and, for each patient participating in the study, promptly record all data in the CRF as required by this protocol.

12.5 **Risks**

This is a non-interventional observational study. It does not involve any direct patient intervention with respect to laboratory tests, examinations or drug treatment. Patients will be asked to complete questionnaires related to their RA, QoL, functioning, work productivity, treatment satisfaction, and healthcare resource utilization at their clinic during their visit three times over the course of 6 months, requiring approximately 30 minutes of their time each time.

12.6 **Discontinuation or Drop-out**

Patients' participation in the study is completely voluntary, and they are allowed to withdraw or discontinue from the study. The following three situations will be counted as study drop-out:

- 1) Patient is switched off Adalimumab
- 2) Patient is not willing to continue participation in the study
- 3) Patient disappears and cannot be contacted anymore

For the first two situations, the Early Termination Form (Appendix K) will be provided for the patients and their physicians to fill in.

Patients not completing questionnaires will not be classified as drop-out. For example, if a patient missed Week 12 questionnaires for some reason, he/she can still fill in Week 24 questionnaires.

Once a subject is dropped out from the study, no further information for that subject will be collected. However, the reason for drop-out will be collected and, if the reason for treatment discontinuation is due to an adverse event, the event will be reported to Abbvie within 24 hours of physician awareness.

12.7 **Quality control and audit**

Steps to be taken to ensure the accuracy and reliability of data include the selection of qualified investigators and appropriate study centers, review of protocol procedures with the investigator and associated personnel before the study and periodic monitoring visits by the sponsor. Written instructions will be provided for administration and collection of study questionnaires.

Guidelines for CRF completion will be provided and reviewed with study personnel before the start of the study. The sponsor will review CRFs and patient questionnaires for accuracy and completeness during on-site monitoring visits and after transmission to the sponsor; any discrepancies will be resolved with the investigator or designee, as appropriate. After upload of the data into the clinical study database they will be verified for accuracy and consistency with the data sources.

The study will be performed following the IMS and AbbVie Standard Operating Procedures (SOPs) for Observational Studies.

12.8 **Communication of findings**

AbbVie / IMS shall retain ownership of all screeners, case report forms, data analysis, and reports which result from this study.

All information obtained as a result of the study will be regarded as confidential, until appropriate analysis and review by AbbVie and the investigator(s) are completed. The results of the study may be published or presented by the investigator(s) after the review by, and in consultation and agreement with AbbVie, such that confidential or proprietary information is not disclosed.

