9.0 Research Methods

9.1 Study Design

This study is designed as a prospective, observational study to assess the effect of adalimumab on health-related QoL and work productivity in patients with RA in Taiwan in clinical practice.

Note: This study is non-interventional and the subjects/investigators will follow the current clinical practice in each site and also the routine clinical follow up as determine by the treating physician.

This study is non-interventional. Patient therapy is not decided by the study protocol but falls within current medical practice, and the prescription of adalimumab is clearly separated from the decision to include the patient in this study. The subjects/investigator will follow the current clinical practice in each site and also the routine clinical follow up as determine by the treating physician.

RA patients will be recruited from within the clinical settings of each rheumatologist participating in the study. Approximately 100 patients diagnosed with RA that meet the inclusion and exclusion criteria will be enrolled at approximately 7 sites in Taiwan.

To assess health and disability outcomes, the HAQ DI at baseline, Week 12 and Week 24 after treatment initiation with adalimumab will be collected. In addition, other PROs of work activity and well-being, including the WPAI, EQ-5D, and SF-36, will also be collected. All above instruments have been validated for the Chinese version.

The HCRU will also be collected. This includes surgical procedures, hospitalizations, bed days in hospital, physician consultations etc. Costs will be assigned based on the HCRU using standardized costs for each participating centers.

The patients identified by the recruiting investigators based on the study selection criteria will be collected data as observed on QoL, functioning, work productivity,

treatment satisfaction, impression of change and HCRU. Data will be captured at baseline (D0), Week 12 and Week 24.

Subjects may discontinue adalimumab treatment at any time during study participation. Subjects that end study participation early will have a Termination Visit, which may be a routine follow-up visit at investigator's clinic. All subjects will have a data recorded approximately 70 days after the Week 24 dosing or after the last administration of adalimumab to obtain information on any new or ongoing AEs.

Primary Endpoint Analysis

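### Protocol 12.6 ends data collection at drop-out, which includes stopping adalimumab, and so contradicts the 70-day adverse event and 150-day pregnancy follow-up required elsewhere

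*Protocol*

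**What the plan says.** Protocol 12.6 lists three situations that count as drop-out. The first is "Patient is switched off Adalimumab"; the others are unwillingness to continue and loss of contact. It then gives the general rule: "Once a subject is dropped out from the study, no further information for that subject will be collected".

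The same section keeps three items:
- The termination form: "For the first two situations, the Early Termination Form (Appendix K) will be provided for the patients and their physicians to fill in".
- The reason for drop-out.
- An adverse event that led to stopping, which must be reported: "However, the reason for drop-out will be collected and, if the reason for treatment discontinuation is due to an adverse event".

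Other sections ask for data after the last dose:
- **9.1:** "Subjects that end study participation early will have a Termination Visit", and "All subjects will have a data recorded approximately 70 days after the Week 24 dosing or after the last administration of adalimumab". The observation periods at the end of 9.1 run to 70 days for safety and 150 days for pregnancy.
- **9.2.6:** for subjects who dropped out early, terminal visit data within 2 weeks of the last dose, then a record at about 70 days of new or ongoing adverse events.
- **11.1.4:** "Subjects will be contacted approximately 70 days following the intake of the last dose of physician-prescribed treatment".
- **11.1.6:** "Pregnancies will be collected from the date of the first dose through 150 days following the last dose of adalimumab", together with the outcome of the pregnancy.
- **Table 1:** a column for early termination or drop-out covering DAS28 and the patient questionnaires, and columns at 70 and 150 days after Week 24 or the last dose.

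**The concern.** A patient who stops adalimumab is a drop-out under 12.6, and stopping is also what starts the 70-day and 150-day periods. The rule that closes the record and the rules that keep it open are therefore triggered by the same event in the same patient. Under 12.4 the investigator agrees to follow the protocol, and no section says which text prevails.

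A site that follows 12.6 as written would miss a serious adverse event that arises after stopping, or one that was present but was not the reason for stopping. It could also miss a pregnancy detected after the last dose, or the outcome of a pregnancy that led to withdrawal. Two sites could each follow the text and ascertain safety differently in the patients who stopped. A contact missed at the time may not be recoverable later.

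There is also a smaller analysis issue. The comparison of HAQ DI change between continuing and withdrawn patients (Protocol 9.7.6; SAP 2.3 and 5.3) needs HAQ DI values from patients who stopped.

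**Working it through.** The plan states no figure for this point, so the check is a comparison of texts plus a simple count.

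**Step 1. Does any section exempt drop-outs from the later collection?** No. The record in 9.1 is for all subjects. Section 9.2.6 is written specifically about subjects who dropped out prematurely. Sections 11.1.4 and 11.1.6 count from the last dose without exception, and Table 1 times its last two columns from Week 24 or the last dose.

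**Step 2. Do the items kept by 12.6 cover what the other sections require?**

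| Required elsewhere | Kept by 12.6? |
|---|---|
| New or ongoing adverse events at about 70 days (9.1, 9.2.6, 11.1.4) | Only an event that caused discontinuation |
| Pregnancies to 150 days after the last dose (9.1, 11.1.6) | No |
| Pregnancy outcome (11.1.6) | No, if withdrawal for pregnancy counts as drop-out |
| Termination visit (9.1, 9.2.6) | Partly, through the Early Termination Form |
| Patient-reported outcomes at early termination (Table 1) | Unclear |

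The first three rows are the contradiction. On the third, 9.2.6 withdraws a pregnant subject immediately, while 11.1.6 asks for an outcome that will usually be known only later.

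The fourth row is not a firm conflict. The clinician's form records joint counts, ESR or CRP, DAS28, surgery, adalimumab use and stop date, and medication. The patient's form records resource use.

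The fifth row is open. The pages of Appendix K available to me contain none of the HAQ DI, SF-36, EQ-5D, WPAI, PGIC or satisfaction items, but the end of the form was not available. Protocol 9.7.9 and SAP 3.5.5 add to the doubt by saying that efficacy measures are not assessed after adalimumab stops.

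**Step 3. One patient under both rules.** Assume, for illustration, a last dose at Week 12, day 12 × 7 = 84.
- Under 9.2.6, terminal visit data are due by day 84 + 14 = 98.
- Under 9.1, 9.2.6 and 11.1.4, the adverse event record falls at about day 84 + 70 = 154.
- Under 11.1.6, pregnancies are collected to day 84 + 150 = 234.
- Under 12.6, nothing is collected after drop-out beyond the three kept items. The day 154 record and the day 234 limit have no counterpart.

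**Step 4. How many patients could be affected?** The only inputs are the planning drop-out rates, applied to about 100 recruits.
- Protocol 9.5, 10%: 100 × 0.10 = 10.
- SAP section 4, 13%: 100 × 0.13 = 13. The SAP's bracket of 10% to 15% gives 10 to 15.

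These rates cover all drop-outs. They do not separate patients switched off adalimumab from those unwilling or out of contact, and the documents give no split.

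**The case against.** The strongest reply is that the conflict is narrow and has little effect on the reported results.

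- **Section 11 is the designated place for adverse events.** Sections 9.2.4 and 9.2.5 send the reader there, and 11.1.4 gives the 70-day contact without exception. A careful site may follow it. This makes loss of data less likely, but 12.6 remains an unqualified instruction and nothing ranks the two.
- **The planned safety analysis covers events on adalimumab (9.7.7), and non-serious events are not actively solicited (11.1.1).** Both are correct, so the safety tables may change little. The protocol still requires serious events and pregnancies to be collected after the last dose.
- **The primary endpoint is unaffected.** This stands: it is the HAQ DI change in patients who continue adalimumab.

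A reader might go further and infer that 12.6 stops all collection, that it flatly contradicts the termination visit, and that 10 to 13 patients would have no follow-up at all. The documents do not support this:
- Section 12.6 keeps three items, and its rule can be read as starting once the termination assessment is done. Section 9.1 allows the termination visit to be a routine one.
- The words about all subjects attach only to the 70-day record. The 150-day rule is a collection period for pregnancies.
- The 10% and 13% are sample-size allowances. They include patients who cannot be contacted under any wording and patients who are unwilling to continue. For pregnancy they also include patients not of childbearing potential.

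**Conclusion.** The point holds as an internal inconsistency that is wrong as written, rather than a debatable design choice. Section 12.6 cannot be followed together with the 70-day adverse event follow-up or the 150-day pregnancy collection and outcome. Against the early-termination questionnaires in Table 1, including the HAQ DI for the withdrawal comparison, it is unclear rather than contradictory.

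The size is at most about 10 to 13 of 100 patients at the planning rates of 10% and 13%, and fewer after the exclusions noted above. This assumes that actual drop-out resembles the planning rates. The pregnancy-outcome part also assumes that withdrawal for pregnancy is treated as drop-out under 12.6. Whether sites would in fact diverge cannot be known from the documents; the text allows it.

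**What to change.** Reconcile 12.6 with 9.1, 9.2.6, Table 1, 11.1.4 and 11.1.6. For each of the three drop-out situations (switched off adalimumab, unwilling to continue, out of contact), 12.6 should state which data are still collected and until when. It should cover:
- the termination form and visit;
- the Table 1 questionnaires at early termination, including the HAQ DI;
- the 70-day adverse event record or contact;
- pregnancies to 150 days and their outcome, saying whether withdrawal for pregnancy is a drop-out.

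For patients out of contact, the text should also agree with the tracing attempts in 9.2.6. If the HAQ DI is not to be collected at termination, the observed-versus-withdrawal comparison in Protocol 9.7.6 and SAP 5.3 needs to say what data it will use.

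Which rule prevails is for the sponsor to decide. The cost is a wording amendment, because the contacts are already required elsewhere in the protocol.
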